## **2.2. Randomization and Blinding**

This is a non-randomized OL extension study that includes patients who previously completed a Teva-sponsored double-blind, placebo-controlled study (Studies 30025 or 30027) of sc administration of reslizumab in severe eosinophilic asthma. So, no randomization or blinding will be performed.

## **2.3. Data Monitoring Committee**

There will be no Data Monitoring Committee in this study.

## **2.4. Sample Size and Power Considerations**

The sample size for this study is not based on power considerations. The sample size is determined by the number of patients anticipated to rollover from the 2 double-blind, placebo-controlled, Phase 3 studies of reslizumab sc (Studies 30025 and 30027).

Approximately 360 patients will be enrolled in this study. The objective of this study is primarily safety oriented; therefore, no formal hypothesis testing is planned. Patients completing at least the full treatment periods of Studies 30025 and 30027 (or through at least the early follow-up visit for adolescents from Study 30025) and meeting the protocol's inclusion criteria and none of the exclusion criteria are eligible for enrollment in this study. It is estimated that the majority of patients enrolled in eligible reslizumab safety and efficacy studies will rollover to this study.

## **2.5. Sequence of Planned Analyses**

### **2.5.1. Planned Interim Analyses**

There will be a planned data cut will be produced before the supplemental Biologics License Application (sBLA) submission. For the purpose of this analysis, a data cut-off will be established in accordance with the targeted date of submission and an interim CSR will be prepared. All outputs identified in this SAP and planned for the final analysis (Section 2.5.2) will be prepared at this time. The interim CSR to support sBLA submission will be based on all data accumulated from the study start to December 2017.

An additional planned data cut will be produced before the Day 120 safety update report, following the sBLA submission. For the purpose of this analysis, a data cut-off will be established in accordance with the targeted date of submission and safety data from this study

will be integrated with safety data from the other studies within the Day 120 report (in this case, there will be no separate interim CSR). The summaries provided at the time of this data cut will be consistent with those planned for the Summary of Clinical Safety (SCS) in the sBLA.

At the time of each planned interim analysis, no individual patient's data are considered fully locked; therefore interim results are interpreted as preliminary.

### **2.5.2. Final Analyses and Reporting**

All final, planned analyses identified in this SAP will be performed after the last patient has completed the study and the database has been locked. The final study report will include all study population, efficacy, safety, and immunogenicity data as specified in the protocol and this analysis plan.

### **3. ANALYSIS SETS**

#### **3.1. Enrolled Analysis Set**

The enrolled analysis set will include all enrolled patients, regardless of whether or not a patient took any dose of reslizumab. A patient is considered enrolled if informed consent form is obtained. The set of enrolled patients will be used for study population summaries.

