Adverse event inquiry	X		X ^c	X	X	X	X	X	X	X	X	X	X	
Concomitant medication inquiry ⁱ	X		X ^c	X	X	X	X	X	X	X	X	X	X	
IMP administration			X	X	X	X	X	X	X	X	X			
Injection site assessment ^j			X	X	X	X	X	X	X	X	X			

^a Visit 1 (screening/baseline) will take place at the EOT visit for patients seamlessly rolling over from Studies 30025 and 30027. Any patient who did not rollover seamlessly from Study 30025 or 30027 will be seen first at an earlier screening visit (V0) in order to complete informed consent and eligibility criteria procedures before completing all other procedures and IMP administration at V1. Adolescents (a patient 12 through <18 years of age) from Study 30025 can complete the V0 screening visit of Study 30066 the same day as the 12 week early follow up visit for Study 30025. Additionally, any patient who did not rollover seamlessly from Study 30025 or 30027 will participate in a 7-day run-in period where baseline measures for asthma control and spirometry will be established. The screening period (including run in) will be up to a maximum of 14 days. Patients who complete the screening assessments of informed assent/consent, medication history, and inclusion and exclusion criteria at V0 do not need to repeat them at V1. Any assessments that are performed at V0 do not need to be repeated at V1 if completed within the previous 14 days (including blood tests completed by adolescents at the 12 week early follow up visit for Study 30025).

Clinical Study Protocol

Open-Label Extension Study—Eosinophilic Asthma Study C38072-AS-30066

^b Beta-human chorionic gonadotropin serum pregnancy tests will be performed at V0 for patients who did not seamlessly rollover (female patients who are not postmenopausal or surgically sterile only). Urine pregnancy testing will be performed at all other visits for all female patients who are not postmenopausal or surgically sterile only. Note: FSH level will be obtained from serum chemistry test as required to determine postmenopausal status. Please see the Laboratory Manual for further information.

^c These assessments may have been done as part of the EOT visit of Study 30025 or 30027 if patient seamlessly enters open-label study.

^d If a potentially clinically significant CPK level ($\geq 3.1 \times$ ULN) occurs, please refer to Protocol Section 7.1.6.1.2 for further management.

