4.6. Screening Failure

Screening failures are defined as participants who consent to participate in the clinical study but are not subsequently enrolled in the study. Minimum information to be collected includes, but is not limited to, demography, screening failure details, eligibility criteria, and any serious adverse events.

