9.2. Analysis Sets

9.2.1. Enrolled Analysis Set

The enrolled analysis set will include all enrolled patients, regardless of whether or not a patient took any dose of reslizumab. A patient is considered enrolled according to the status reported in the database. The set of enrolled patients will be used for study population summaries.

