9.4.1. Patient Disposition

Data from patients screened, from patients screened but not treated, from patients in the safety analysis set, from patients who completed the study, and from patients who withdrew from the study will be summarized using descriptive statistics. Data from patients who withdrew from the study will also be summarized by reason for withdrawal.

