## 5. STUDY POPULATION

### 5.1. General

The enrolled analysis set (Section 3.1) will be used for all study population summaries, unless otherwise specified. Summaries will be presented by double-blind treatment group in the previous studies 30025 or 30027 (placebo and reslizumab) and for all patients (ie, total), unless otherwise noted.

For continuous variables, descriptive statistics (number of patients [n], mean, standard deviation [SD], standard error [SE], median, minimum, and maximum) will be provided. For categorical variables, patient counts and percentages will be provided. Categories for missing data will be presented if necessary.

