### 5.2. Patient Disposition

Data from patients enrolled, patients enrolled but not treated, patients in the safety analysis set, patients who completed the treatment, patients who completed the study, patients who discontinued from treatment, and patients who withdrew from the study will be summarized using descriptive statistics. Data from patients who discontinue from the treatment and patients who withdrew from the study will also be summarized by reason for withdrawal. The previous study from which patients enrolled (30025 or 30027) will also be summarized, along with whether the patient was a seamless rollover or non-seamless rollover. This summary will include all patients enrolled into this study. The denominator for calculating the percentages will be the number of enrolled patients as appropriate.

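### SAP 3.1 counts every consented patient as enrolled, contrary to Protocol 4.6, so screening failures enter the enrolled set and treated-patient percentages such as completion are understated

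*SAP*

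**What the plan says.** SAP 3.1 sets the rule for the enrolled analysis set: "A patient is considered enrolled if informed consent form is obtained".

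Protocol 4.6 treats consent and enrolment as different steps: "Screening failures are defined as participants who consent to participate in the clinical study but are not subsequently enrolled in the study". Protocol 9.2.1 defines the same analysis set by another criterion: "A patient is considered enrolled according to the status reported in the database". It does not describe how that status is assigned.

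SAP 5.1 says that the enrolled set "will be used for all study population summaries, unless otherwise specified". That covers demographics, medical history, prior medication, baseline ECG and examination, and protocol violations (SAP 5.3 to 5.9). For disposition, SAP 5.2 adds: "The denominator for calculating the percentages will be the number of enrolled patients as appropriate".

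The disposition rows differ between the documents. Protocol 9.4.1 begins: "Data from patients screened, from patients screened but not treated, from patients in the safety analysis set". SAP 5.2 begins: "Data from patients enrolled, patients enrolled but not treated, patients in the safety analysis set, patients who completed the treatment". Neither has a row for screening failures.

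The SAP Introduction gives the SAP precedence where the documents differ and leaves the explanation to the clinical study report. SAP Section 14, Table 7 lists one change from the protocol, the additional data cut for the Day 120 safety update.

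**The concern.** Under SAP 3.1 nobody can consent and remain unenrolled, so the category that Protocol 4.6 defines would be empty. The SAP also sits awkwardly with its own Section 2.4, where patients who meet the criteria become eligible for enrolment, which places enrolment after the eligibility check.

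The design allows for screening failures. Patients who do not roll over seamlessly attend a separate visit V0 "in order to complete informed consent and eligibility criteria procedures before completing all other procedures and IMP administration at V1" (Protocol Table 1, footnote a). The exclusion for a recently treated exacerbation applies only to them, and Protocol 4.5 gives it a rescreening rule. Adolescents from Study 30025 must first complete a 12-week visit off study drug, so they take this route too.

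At stake are the disposition and baseline tables. The protocol synopsis, under Tolerability Analysis, names patient disposition alongside the on-treatment safety profile as the evidence on tolerability. A completion percentage diluted by people who were never eligible says less about tolerability than it appears to. With no screening-failure row, an ineligible patient also cannot be told apart from an eligible patient who was never dosed.

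**Working it through.** **Is there a plan figure to reproduce?** The planned number is approximately 360 enrolled (Protocol 9.1, SAP 2.4). It is a rollover estimate with no formula, so there is nothing to re-derive. The check is denominator arithmetic.

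**Inputs.**
- E = 360 enrolled in the Protocol 4.6 sense (from the documents).
- f = screening failures as a share of consented patients. Not in the documents; assumed 2% to 20%, with 5% to 10% as the illustration.
- All 360 are dosed and 90% complete treatment, so 324 complete. Both are assumptions.

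**Formulas.** Consented patients C = E / (1 − f), rounded up. Screening failures S = C − E. A row whose numerator holds only treated patients has percentage x/E under Protocol 4.6 and x/C under SAP 3.1. The ratio is E/C = 1 − f.

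| f | C | S | Safety set (360/C) | Completed (324/C) | Enrolled, not treated (S/C) |
|---|---|---|---|---|---|
| Excluded (Protocol 4.6) | 360 | n/a | 100% | 90.0% | 0% |
| 2% | 368 | 8 | 97.8% | 88.0% | 2.2% |
| 5% | 379 | 19 | 95.0% | 85.5% | 5.0% |
| 10% | 400 | 40 | 90.0% | 81.0% | 10.0% |
| 20% | 450 | 90 | 80.0% | 72.0% | 20.0% |

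**Rows that do not fall.**
- Enrolled stays at 100% by construction.
- Enrolled but not treated rises, as in the last column.
- Withdrawal can move either way. Take the 36 non-completers as withdrawals (10.0% of 360). At f = 10% the row reads 36/400 = 9.0% if screening failures are not counted as withdrawals, and (36 + 40)/400 = 19.0% if they are.
- The rollover-type shares still sum to 100%. Assuming 60% seamless (216 of 360) and all 40 failures non-seamless, seamless goes to 216/400 = 54.0% and non-seamless to (144 + 40)/400 = 46.0%.

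**If 360 is read as the number consented**, the treated number is 360 × (1 − f): 342 at 5% and 324 at 10%.

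**The case against.** The strongest defence is that the SAP has mostly relabelled rows. If enrolled means consented, its first two disposition rows match the protocol's screened and screened-but-untreated rows almost one for one, and Protocol 9.4 itself assigns that screened-based table to the enrolled set. The protocol's own usage is therefore unsettled. The safety-set count is also a row, so a reader can recompute completion among treated patients; the SAP allows discretion on the denominator; and the Introduction promises that differences will be explained in the study report. All of this limits the harm. It does not reconcile SAP 3.1 with Protocol 4.6, and denominator discretion in SAP 5.2 does not change who is in the set used for the other tables.

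Some stronger readings are tempting but unsupported:
- A reader might infer that every disposition percentage falls. The arithmetic shows otherwise.
- A reader might infer a proven conflict with Protocol 9.2.1. The database status is undefined there, so only a different criterion is shown; the conflict is with Protocol 4.6.
- A reader might infer that rescreened patients are counted twice. Nothing says that they consent again, and SAP 3.1 is worded per patient.
- A reader might infer that the whole baseline table is contaminated. SAP 4.2 generally ties baseline to the first dose in this study, so a never-dosed patient has no defined baseline for spirometry, OCS dose, ECG or examination and would appear as a lower n or as missing. The effect falls mainly on demographics and medical history.

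**Conclusion.** The definition in SAP 3.1 is wrong as written. It contradicts Protocol 4.6, takes precedence over it, and is not declared in Table 7. Percentages limited to treated patients are understated by the factor 1 − f, and the enrolled-but-not-treated row is inflated by ineligible patients.

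The size cannot be known from the documents. The fall in completion from 90% to 85.5%–81.0% rests on an assumed 90% completion and an assumed 5% to 10% screening failure. The true effect may be small, since all patients come from two parent studies and seamless patients consent at V1 rather than at a separate screening visit.

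Severity is minor. SAP 3.2 bases safety and efficacy summaries on patients who received at least one dose, so the primary endpoint and all secondary summaries on that set are untouched, and the study tests no hypothesis.

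**What to change.** - **SAP 3.1:** define an enrolled patient as one who consented, is not a screening failure, and is recorded as enrolled in the database. Do not add a requirement to have met all eligibility criteria. Protocol Appendix C foresees patients entered in violation of the criteria. Such a requirement would drop them from the enrolled set and from the violation summary in SAP 5.9, while any who were dosed would remain in the safety set.
- **SAP 5.2:** add two count rows, patients screened (as in Protocol 9.4.1) and screening failures, with each patient counted once. The screening-failure row is new; the protocol's list does not have one.
- **SAP Table 7:** list any difference from the protocol that remains.

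The cost is one sentence, two table rows and, if needed, one entry in Table 7. No new data are required, because Protocol 4.6 already has screening-failure details collected.

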#### **3.2. Safety Analysis Set**

The safety analysis set will include all patients who received at least 1 dose of reslizumab in this study. The primary analysis population for both safety and efficacy summaries will be the safety analysis set.

#### **3.3. Subgroup Analysis Sets**

Selected efficacy and safety endpoints including clinical asthma exacerbations, FEV1, [REDACTED] and adverse events will be summarized separately for seamless and non-seamless rollover patients.

## 4. GENERAL ISSUES FOR DATA ANALYSIS

### 4.1. General

Descriptive statistics for continuous variables include number of patients (n), mean, standard deviation (SD), standard error (SE), median, minimum, and maximum. Descriptive statistics for categorical variables include patient counts and percentages, missing categories will be presented if necessary.

### 4.2. Specification of Baseline Values

Baseline will be defined as the last observed value prior to the first dose of reslizumab in this study unless otherwise stated below.

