## 1. STUDY OBJECTIVES AND ENDPOINTS

### 1.1. Primary and Secondary Study Objectives and Endpoints

The primary objective of this study is to support the long-term safety of reslizumab 110 mg administered subcutaneous (sc) once every 4 weeks in patients 12 years of age and older with severe eosinophilic asthma that is inadequately controlled on standard-of-care treatment.

The primary endpoint is frequency of all adverse events including serious adverse events.

The secondary safety endpoints for this study include the following:

- clinical laboratory test results – hematology and chemistry results at baseline and at weeks 4 (chemistry only), 8, 24, and 36 or early withdrawal visit
- local tolerability at the injection site at approximately 1 hour after study drug administration every 4 weeks throughout the study
- vital signs measurements every 4 weeks throughout the study
- concomitant medication usage every 4 weeks throughout the study

The secondary objective of this study is to evaluate the efficacy of reslizumab 110 mg administered sc once every 4 weeks in patients 12 years of age and older with severe eosinophilic asthma that is inadequately controlled on standard-of-care treatment.

The secondary efficacy endpoints for this study include the following:

- clinical asthma exacerbation (CAE) and healthcare utilization (HCU)-related endpoints
  - frequency of CAEs
  - frequency of asthma-specific hospital admissions
  - length of hospital stay and number of Intensive Care Unit (ICU) days
  - frequency of asthma-specific emergency department visits
  - frequency of school/work days missed due to asthma
- change from baseline in pre-bronchodilator Forced Expiratory Volume in 1 Second (FEV1) measured using spirometry at weeks 0, 8, 24, and 36 or early withdrawal visit
- change in daily morning ambulatory FEV1 from baseline at each week through week 36 or early withdrawal, as measured by the handheld spirometry device.
- absolute and percent reduction in the daily Oral Corticosteroid (OCS) dose at weeks 20 and 36 or early withdrawal visit as compared with the dose at baseline (for patients on daily OCS at baseline).
- change from baseline in total inhalations of reliever bronchodilator medication (eg, short-acting beta agonist) measured using weekly averages until week 36 or early withdrawal visit.

- change from baseline in Asthma Control Questionnaire (ACQ-6) score performed at weeks 0, 8, 24, and 36 or early withdrawal visit

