#### 4.2.1. Diary

Baseline for diary-based efficacy variables (total reliever bronchodilator medication, █) will be defined as the average of the values over the 7 days preceding the first dose of reslizumab in this study. At least 4 out of the 7 expected measurements need to be recorded for each diary variable; otherwise the baseline value for that variable will be treated as missing. This definition will exclude daily morning ambulatory FEV1 whose baseline value will be derived as outlined in Section 4.2.2.

For non-seamless rollovers, baseline will be derived from data collected in this study during 7-day run-in period prior to Visit 1. For seamless rollovers, baseline will be derived from data collected during the 7 days preceding the EOT visit of the previous study (30025 or 30027).

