#### 4.2.2. Spirometry

Pre-bronchodilator FEV1 at pre-specified clinic visits and daily morning ambulatory FEV1 will be measured using a handheld device that has combined spirometry and eDiary capabilities.

The baseline value for pre-bronchodilator FEV1 measured at the clinic visits will be the last observed value prior to the first dose of reslizumab in this study. The baseline value for daily morning ambulatory FEV1 will be defined similarly.

For non-seamless rollovers, baseline will be derived from data collected in this study on or prior to Visit 1. For seamless rollovers, baseline will be derived from data collected at the EOT visit of the previous study (30025 or 30027).

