#### 4.2.3. Patient Reported Outcomes

The baseline value for patient reported variables (ACQ-6, AQLQ +12) will be the last observed value prior to the first dose of reslizumab in this study.

For non-seamless rollovers, baseline will be derived from data collected in this study on or prior to Visit 1. For seamless rollovers, baseline will be derived from data collected on the same day as the EOT visit of the previous study (30025 or 30027).

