**4.2.4. Oral Corticosteroid Dose**

The baseline value will be defined as the OCS dose reported on the day of first dose of reslizumab in this study.

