**4.2.7. ADA**

The baseline value for all ADA status will be the last observed value prior to the first dose of reslizumab in the previous double-blind study (30025 or 30027).

For both seamless and non-seamless rollovers, baseline will be derived from data collected on the same day as the day of randomization (DOR) visit of the previous study (30025 or 30027).

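### Change in efficacy variables and eosinophils is taken only from the extension baseline, so former-reslizumab patients are never compared with their untreated state and the all-patients change mixes unlike quantities

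*SAP*

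**What the plan says.** The general baseline rule is in SAP 4.2: "Baseline will be defined as the last observed value prior to the first dose of reslizumab in this study unless otherwise stated below". Protocol 9.5.2 anchors clinic and diary efficacy variables at the same time. SAP 4.2.1 to 4.2.5 then give the source of each value:

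- **FEV1 (4.2.2):** "For seamless rollovers, baseline will be derived from data collected at the EOT visit of the previous study (30025 or 30027"). Patients with a gap use values collected in this study up to Visit 1.
- **Reliever use (4.2.1):** the 7 days before the parent end-of-treatment visit for seamless patients, and the run-in week for the others.
- **ACQ-6, AQLQ12+ and eosinophils (4.2.3, 4.2.5):** the day of the parent end-of-treatment visit for seamless patients.
- **OCS dose (4.2.4):** "The baseline value will be defined as the OCS dose reported on the day of first dose of reslizumab in this study".

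Only immunogenicity goes back to the untreated state. SAP 4.2.7 reads: "The baseline value for all ADA status will be the last observed value prior to the first dose of reslizumab in the previous double-blind study".

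SAP 1.1 states the aim: "The secondary objective of this study is to evaluate the efficacy of reslizumab 110 mg administered sc once every 4 weeks". SAP 2.1 adds that the asthma control measures are there to assess the long-term effect. SAP 6.1 presents efficacy by previous double-blind arm and in total. SAP 3.3 adds a split by rollover type for selected endpoints, including exacerbations and FEV1.

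**The concern.** One column label, change from baseline, covers three different starting states. For a seamless former-reslizumab patient the starting value already contains whatever the drug did in the parent study. A change near zero then fits two accounts: an effect that is fully maintained, or no change from the untreated level at any time. These patients have the longest exposure, so they bear most directly on long-term effect.

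Two variables have an added problem:

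- **OCS.** SAP 6.3.3.2 restricts the summary to patients on daily OCS at the extension baseline. Any former-reslizumab patient who came off OCS during the parent study is left out, so the largest reductions would not be counted.
- **Eosinophils.** SAP 10.1 plans percent change. In seamless former-reslizumab patients the denominator is already lowered by the drug, so the percentage cannot show depletion and may be unstable.

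**Working it through.** The plan gives no figure to reproduce. The sample of about 360 is the expected rollover, with no power basis (SAP 2.4), and the analyses are descriptive (protocol 9.5.2).

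**Step 1: drug status at the extension baseline.** Protocol 1.2.2.1 gives a terminal half-life of about 26 days after sc dosing and a range of mean elimination half-lives of 23 to 30 days. Assumptions: single-exponential decay, and a parent end-of-treatment visit 4 weeks after the last parent dose.

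Fraction remaining = 0.5^(days / half-life).

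- 4 weeks (28 days), seamless: 0.5^(28/26) = 0.47, range 0.43 to 0.52.
- 16 weeks (112 days), Study 30025 adolescents after their 12-week follow-up: 0.5^(112/26) = 0.05, range 0.03 to 0.08.

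Protocol 1.2.2.2.4 reports mean eosinophil counts back at baseline 4 months after the last dose in the iv studies. So seamless patients are on drug, and those with a long gap may be largely off it. Gap length is to be summarized (SAP 8.2), but no length is stated.

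**Step 2: what the change then means.**

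| Patients | State at extension baseline | What the change shows |
|---|---|---|
| Former reslizumab, seamless | On drug | Persistence or further change |
| Former reslizumab, with a gap (including such adolescents from 30025) | Possibly largely off drug | Change on retreatment, depending on gap length |
| Former placebo | Untreated | First change on drug |

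**Step 3: the all-patients column.** Let p be the share of former-reslizumab patients and r their average extension change divided by the former-placebo change. Then:

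pooled change / former-placebo change = (1 - p) + p × r.

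Neither p nor r is in the documents. Over assumed values:

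| p | r = 0 | r = 0.25 | r = 0.5 |
|---|---|---|---|
| 1/3 | 67% | 75% | 83% |
| 1/2 | 50% | 63% | 75% |
| 2/3 | 33% | 50% | 67% |

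For example, p = 2/3 with r = 0 gives 1/3 + 0 = 33%; p = 1/3 with r = 0.5 gives 2/3 + 1/6 = 83%.

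**Step 4: do other planned displays supply the missing reference?**

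- Actual values are planned for FEV1, reliever use, ACQ-6, AQLQ12+ and eosinophils (SAP 6.3.2.2, 6.3.4.2, 6.3.5.2, 6.3.6.2, 10.1). They start at the extension baseline, so the parent pre-treatment level does not appear.
- For OCS, the endpoint analysis gives only absolute and percent change (SAP 6.3.3.2).
- The prior-arm split separates former placebo from former reslizumab. Within the latter, seamless and gap patients stay together unless rollover type is crossed with arm, which SAP 3.3 does not state.

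**The case against.** The strongest reply is that the extension baseline is the natural one for an extension, is prespecified in both documents, and serves a secondary descriptive aim in a safety study. Whether reslizumab works is a question for the randomized parent studies. Change since the parent baseline would be one more uncontrolled before-after difference. All of that stands, and it is why the extension baseline should be kept and the addition called supplementary.

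The reply also rules out several stronger readings that a reader might infer:

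- *The efficacy objective cannot be answered.* The documents do not support this. Exacerbation and healthcare-use frequencies are counted over the treatment period and need no baseline (SAP 6.3.1.2). Actual values are shown for most other variables, and the objective names no reference point.
- *Durability cannot be read from any table.* For seamless former-reslizumab patients, change since the parent end-of-treatment visit is a direct description of persistence.
- *All former-reslizumab patients are on drug at baseline.* Those with a gap, including the 30025 adolescents among them, may not be.
- *The efficacy results as a whole are diluted.* Only the total column is. The prior-arm columns stand beside it, and the mean-change line graphs are by prior arm.
- *The loss can be stated in litres.* The 0.129 L in protocol 5.3.1 comes from 0.3 mg/kg iv at week 16. It is not an effect of 110 mg sc.

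The seamless/gap split helps for FEV1, and a redaction in SAP 3.3 means that more endpoints may be covered. It still gives no untreated reference.

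**Conclusion.** The point holds as a limit on interpretation. For the six variables named, no planned change summary gives former-reslizumab patients a comparison with their untreated state, although the plan makes that link for ADA. The OCS restriction and the eosinophil percent change follow from the same choice.

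The pooled change would be about 33 to 83% of the former-placebo change. This is illustrative: it rests on an assumed p of 1/3 to 2/3 and r of 0 to 0.5. If many former-reslizumab patients restart after a long gap, r could be higher and the shortfall smaller. How many patients the OCS restriction removes cannot be computed from the documents.

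**What to change.** Keep the extension baseline as planned and add the following to the SAP:

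1. A supplementary descriptive summary of change from the last value before the first dose in the parent study, by prior arm and rollover type, for FEV1, reliever use, ACQ-6, AQLQ12+, OCS dose and eosinophils.
2. For that OCS summary, include patients on daily OCS at the parent baseline, whether or not they were still taking it at extension entry.
3. A footnote on every all-patients change from extension baseline, saying that it combines patients with different prior treatment and is not interpretable as a drug effect.
4. A device footnote for clinic FEV1. Under protocol Appendix B, seamless Visit 1 values come from centralized spirometry and later visits use the handheld device.

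This is a cheap improvement: SAP wording and extra tables, with no new visits or samples. It relies on parent baseline values being available. That is a reasonable inference, because parent end-of-treatment values and parent ADA samples are already used, but the documents do not state it. The added change remains an uncontrolled before-after description and should be labelled so.
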